**Statistical criteria**

All statistical calculations will be made using two groups of statistical criteria:

- parametric - to evaluate continuous and interval random values;
- non-parametric – to obtain:
  - evaluations on equality/inequality of proportions of the patients upon their comparison for various visits,
  - analysis of frequencies of the features compared,
 and
  - to evaluate continuous and interval random values in case of non-compliance with normal random distribution.

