### *Evaluation of sample size*

The sample size was assessed in accordance with the following rules and assumptions:

1. Statistical assumptions:

- 1.1 Lack of clinically relevant superiority of reference product (oseltamivir) over test product (Ergoferon) is assumed, thus statistically meeting Non-Inferiority design:

$$\mathbf{H_0: Ef_{control} - Ef_{test} \geq \delta}$$

$$\mathbf{H_A: Ef_{control} - Ef_{test} < \delta,}$$

where  $\mathbf{Ef_{control}}$  – effect of reference product (oseltamivir),  $\mathbf{Ef_{test}}$  – effect of test product (Ergoferon),  $\delta$  – clinically relevant difference;

- 1.2 Clinically relevant difference value “ $\delta$ ” is considered to be equal to 20% (i.e. Ergoferon effect is supposed to be comparable to the one of oseltamivir if the effect of test product is superior to or inferior to the effect of reference product by no more than 20%);
- 1.3 The power of statistical tests ' $P = (1 - \beta)$ ' is 80% (the probability of correct rejection of the null hypothesis is 0.8);
- 1.4 The probability of type 1 error ' $\alpha$ ' is less than 5% (the probability of false acceptance of the alternative hypothesis is less than 0.05);
- 1.5 Therefore, sample size will be calculated taking into account:
- a. assumption on expected effects declared in the main efficacy criterion of the protocol;
- 1.6 calculation of sample size of groups 1 and 2 for two-sided test for final analysis will be made using the formula:

$$\mathbf{N_1=N_2=(p_a(1 - p_a) + p_b(1 - p_b)) I,}$$

where  $\mathbf{N_1}$  and  $\mathbf{N_2}$  – samples sizes in Ergoferon and Oseltamivir groups

$\mathbf{p_a}$  and  $\mathbf{p_b}$  – expected proportions of the patients with recovery/improvement in these groups

$\mathbf{I}$  – Fisher's information detected using the formula:

$$\mathbf{I=(z_\alpha + z_\beta)^2/(\theta - \delta)^2,}$$

where  $\mathbf{z_\alpha}$  and  $\mathbf{z_\beta}$  – tabular values of z-test for  $\alpha$  and  $\beta$ ,  $\theta$  – difference between proportions ( $\mathbf{p_a - p_b}$ ),  $\delta$  – clinically relevant difference;

- 1.7 final sample size will be determined using the formula:

$$\mathbf{N_F = N / (1 - K_B),}$$

---

 SAS/STAT(R) 9.2 User's Guide, Second Edition.

[http://support.sas.com/documentation/cdl/en/statug/63033/HTML/default/viewer.htm#statug\\_seqdesign sect027.htm](http://support.sas.com/documentation/cdl/en/statug/63033/HTML/default/viewer.htm#statug_seqdesign sect027.htm)

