***Non-parametric tests:***

Below are potential types of comparisons with relevant criteria:

1. To evaluate difference in continuous variables obtained in two different (independent) groups – Mann-Whitney test.
2. To evaluate time changes in the parameters compared – Friedman test, nonparametric analogue of repeated measures analysis of variance.
3. For frequency analysis of contingency tables  $2 \times 2$  –  $\chi^2$  (if the frequency under comparison  $> 5$ ) or exact Fisher’s test (if one of the frequencies under comparison  $< 5$ ).
4. Cochran-Mantel-Haenszel test (modified  $\chi^2$  test for multiple comparisons) – to perform frequency analysis based on independent strata.
5. For frequency analysis of data on presence/absence of an event or outcome during repeated measurements (contingency tables with dependent strata) – survival analysis.

To perform the above-mentioned nonparametric statistical analysis the following SAS procedures are to be used:

- FREQ – Friedman test,  $\chi^2$  test and/or exact Fisher's test; Cochran-Mantel-Haenszel test.
- LIFETEST – survival analysis.
- NPAR1WAY - Mann-Whitney test.

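### The plan sets a 20-point non-inferiority hypothesis but lists only tests of equality for proportions, so no stated analysis tests its own null hypothesis

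*Combined protocol and SAP*

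**What the plan says.** In *Evaluation of sample size*, item 1.1 gives the framework: "Lack of clinically relevant superiority of reference product (oseltamivir) over test product (Ergoferon) is assumed, thus statistically meeting Non-Inferiority design". The hypotheses are one-directional: H0 is control minus test ≥ δ, and HA is control minus test < δ. Item 1.2 sets δ at 20% and explains it in two-directional terms: the drugs count as comparable "if the effect of test product is superior to or inferior to the effect of reference product by no more than 20" per cent. Item 1.3 sets power ("the probability of correct rejection of the null hypothesis is 0.8"). Item 1.4 sets type 1 error ("the probability of false acceptance of the alternative hypothesis is less than 0.05"). Item 1.6 refers to "calculation of sample size of groups 1 and 2 for two-sided test for final analysis". The sizing formula subtracts δ from a difference in proportions, so δ means percentage points.

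The margin does not appear after that section:

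- *Statistical criteria* describes the task for proportions as "evaluations on equality/inequality of proportions of the patients upon their comparison for various visits".
- *Non-parametric tests* opens with "Below are potential types of comparisons with relevant criteria". Item 3 ("For frequency analysis of contingency tables") names chi-square or Fisher. Items 4 and 5 name Cochran-Mantel-Haenszel and survival analysis. The SAS list gives FREQ the Friedman, chi-square, Fisher and Cochran-Mantel-Haenszel tests, and nothing else.
- *Parametric criteria* names no margin.
- *Data presentation* plans frequency tables by visit for categorical variables, with no interval estimate.

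**The concern.** As listed, these tests have a null of no difference. Used that way, they can reject the 20-point H0 only by showing Ergoferon superior. The 80% power belongs to a test that the analysis section does not contain.

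Item 1.2 does not fill the gap. It does not say whether the 20% applies to the observed difference or to a confidence limit, and it is two-directional while H0/HA is not. The alpha level is also open: items 1.4 and 1.6 together allow one-sided 5% or one-sided 2.5%.

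This leaves room for two loose readings, neither of which the document adopts: that a non-significant chi-square shows comparability, or that an observed difference within 20 points does. Comparison with oseltamivir is one of the *Study purposes*, and the trial is open-label (*Study design*), so a rule chosen after comparative data are visible would carry little weight.

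**Working it through.** **Inputs from the document.** δ = 0.20, power 80%, type 1 error below 5%, 79 completers per arm, 20% withdrawal. The expected difference is stated as ≥ 0 and is taken here as θ = 0. The expected proportions have symbols but no values, so every response rate below is an assumption.

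**1. The plan's own sample size.** The formula is N per arm = [pₐ(1−pₐ) + p_b(1−p_b)] × (z_α + z_β)² / (θ − δ)².

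- One-sided 5%, common rate 0.5: 0.5 × (1.645 + 0.842)² / 0.04 = 77.3, so 78. This is the largest value over all common rates, so 79 suffices.
- One-sided 2.5%, common rate 0.5: 0.5 × (1.960 + 0.842)² / 0.04 = 98.1, so 99. At 0.6, 0.7 and 0.8 the results are 94.2, 82.4 and 62.8, so 95, 83 and 63.
- Solving for N = 79 at z = 1.960 gives p(1−p) = 0.2013, so p is about 0.72 (or 0.28).
- Withdrawal: 79 / 0.80 = 98.75, so 99 per arm and 198 in total, as stated.

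The figure of 79 is therefore compatible with a margin-based test at either level, depending on the rates. It cannot be reproduced exactly without them.

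**2. Decision rules compared.** Exact enumeration over two independent Binomial(79, p) arms at one binary time point:

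- Chi-square: pooled z, two-sided 5%.
- Score rule (Miettinen-Nurminen): z = (d − 0.20) / √{[p̃_c(1−p̃_c) + p̃_t(1−p̃_t)]/n × 2n/(2n−1)}, where d is observed oseltamivir minus Ergoferon and p̃ are the maximum-likelihood rates constrained to p̃_c − p̃_t = 0.20. The rule is met if z < −1.645 (one-sided 5%) or z < −1.960 (one-sided 2.5%).
- Observed-difference reading of item 1.2: |d| ≤ 0.20. Since 0.20 × 79 = 15.8, this is a gap of at most 15 patients.

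*Truly equal arms:*

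| Common rate | Chi-square favours Ergoferon | Score rule, 5% | Score rule, 2.5% |
|---|---|---|---|
| 30% or 70% | 2.6% | 87% | 79% |
| 40% or 60% | 2.4% | 82% | 73% |
| 50% | 2.3% | 81% | 71% |
| 80% | 2.6% | 93% | 87% |
| 90% | 2.6% | 99% | 98% |

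The chi-square column is the one-direction error of an equality test, not power for non-inferiority.

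*True 20-point deficit (H0 true):*

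| Oseltamivir v Ergoferon | Chi-square non-significant | Observed gap within 20 points | Score rule, 5% | Score rule, 2.5% |
|---|---|---|---|---|
| 60 v 40 | 29.5% | 47.8% | 4.8% | 2.4% |
| 70 v 50 | 27.0% | 47.8% | 4.8% | 2.5% |
| 80 v 60 | 20.5% | 47.7% | 5.1% | 2.6% |
| 90 v 70 | 9.8% | 47.6% | 4.8% | 2.4% |
| 95 v 75 | 3.6% | 47.6% | 4.6% | 2.3% |

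With 99 per arm (a ceiling: every consented patient analysed), the chi-square column becomes 18.0%, 17.4%, 12.3%, 4.6% and 1.2%.

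**3. One possible result.** Oseltamivir 55/79, Ergoferon 44/79. The difference is 11/79 = 13.9 points and the pooled rate is 99/158 = 0.627. Then z = 0.139 / √(0.627 × 0.373 × 2/79) = 1.81 and p = 0.070. Both loose readings pass. The score upper limit is 28.5 points (95% interval) or 26.2 points (90% interval), so the 20-point margin is not excluded at either level.

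Cochran-Mantel-Haenszel and survival analysis were not enumerated.

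**The case against.** The document calls itself a protocol summary and its list of tests potential, so silence should not be read as a decision to test equality. The quoted phrase on proportions is general and does not assign the primary comparison between arms. The sizing formula is that of a margin-shifted z-test, so the intended analysis can largely be inferred. FREQ and GENMOD, both listed, could produce a risk-difference interval. The inflated error rates belong to readings the plan does not adopt, and the chi-square figure drops below 5% near the ceiling. The plan would switch to Fisher for small frequencies. Finally, a preference for score over Wald limits departs from the variance form in the plan's own formula.

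Several of these points stand. The claim is limited to this document, the error rates are conditional illustrations, and their size depends on unknown rates. The Fisher switch changes little: 1.8% rather than 2.6% at equal rates of 90%, and 3.9% rather than 3.6% at 95 v 75.

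The omission remains. A summary detailed enough to name SAS procedures gives none of them the task of testing its only formal hypothesis, and inferring a z-test from the sizing formula does not fix its level. The preference for score limits has numerical support: over control rates of 21–99%, the Wald rule's error reaches 7.0% (nominal 5%) or 4.8% (nominal 2.5%), against 5.2% and 2.7% for the score rule.

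The rule also has to be attached to a named day, source and analysis set. That is a separate matter and does not rescue the text.

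**Conclusion.** The concern holds and must be fixed. The hypothesis that determines the sample size is not tested by any method listed for proportions, and no interval, level or decision rule is stated. This conclusion comes from reading the text and needs no assumed rates.

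The numerical consequences do rest on assumptions: one binary time point, 79 per arm and the response rates shown. On those, a significant chi-square in Ergoferon's favour has almost no chance of establishing what the trial was sized to show when the drugs are equal. The observed-difference reading would accept a true 20-point deficit in nearly half of trials. The non-significance reading would exceed 5% at four of the five rate pairs examined, the exception being 95 v 75. Confidence in the main conclusion is high.

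**What to change.** - State that the primary comparison is the difference in proportions, oseltamivir minus Ergoferon, with a score-type confidence interval (for example Miettinen-Nurminen or Farrington-Manning, not Wald). Conclude non-inferiority only if the upper limit is below 20 percentage points.
- State one alpha: one-sided 5% (90% interval) or one-sided 2.5% (95% interval). If the bound in item 1.4 is strict, use 2.5% or an exact version, because the score rule at 5% can reach about 5.2%.
- Reword item 1.2 to match the one-directional H0/HA, and reconcile the two-sided wording in item 1.6 with the chosen level.
- State that neither a non-significant chi-square or Fisher test nor an observed difference within 20 points is evidence of comparability.

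The cost is text and a little analysis code, to be settled before any comparative look at the data. The choice of alpha can affect the size. At one-sided 5%, 79 per arm suffices at any common rate under the plan's formula. With a 95% interval the sponsor must do one of three things: state assumed rates that support 80% power (a common rate of about 72% or higher, or 28% or lower), restate the power (71–79% at common rates of 30–70%), or enlarge the sample (up to 99 completers per arm at 50%).

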**Parametric criteria**

Prior to analysis using parametric statistics, data samples under comparison will be tested for normality (the Kolmogorov-Smirnov test).

 **Recovery criteria:** body temperature  $<37.0^{\circ}\text{C}$  + no symptoms.

**Improvement criteria:** body temperature  $\leq 37.2^{\circ}\text{C}$  + total symptom score (except for fever index)  $\leq 2$  scores.

The following parameters and approaches are to be used:

1. To evaluate the differences in continuous variables from two different (independent) groups – Student’s test for independent samples.
2. To evaluate differences in continuous variables in one group at two different visits - Student’s test for paired samples.
3. To evaluate time changes in parameters compared - analysis of variance (ANOVA) or modified repeated measures covariance (ANCOVA).
4. In case of multiple comparisons of the groups various corrections for multiplicity will be used, e.g. Dunnett, Tukey, Scheffe, Holm adapted test, etc.
5. In case of abnormal data distribution generalized linear models and/or mixed linear models will be used.
6. Selection of the type of distribution, specification of factor and covariance structures of the model will be made using fit-statistics such as AIC (Akaike information criterion).

The following SAS software programs are supposed to be applied to the above listed tests and techniques:

- UNIVARIATE: normality verification of the distributions under comparison
- CORR, MEANS - calculation of descriptive statistics
- TTEST – Student’s test with all modifications
- GLM – generalized linear models for analysis of time changes (ANOVA, ANCOVA)
- GENMOD – generalized linear models
- MIXED – mixed linear models.

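### For non-normal secondary outcomes the plan states two conflicting analysis rules, does not rank them, and lets fit statistics choose distribution and factors from the outcome data, so the nominal 5% is not assured

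*Combined protocol and SAP*

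**What the plan says.** The gate is in the combined protocol and SAP, under Parametric criteria: "Prior to analysis using parametric statistics, data samples under comparison will be tested for normality". The test named is Kolmogorov-Smirnov, and no significance level is given for it.

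Two sections then say what happens to data that fail.

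- Statistical criteria gives as one use of the non-parametric group "to evaluate continuous and interval random values in case of non-compliance with normal random distribution". Non-parametric tests names the methods. Item 1 reads: "To evaluate difference in continuous variables obtained in two different (independent) groups – Mann-Whitney test". Item 2 reads: "To evaluate time changes in the parameters compared – Friedman test, nonparametric analogue of repeated measures analysis of variance". The list is introduced with "Below are potential types of comparisons with relevant criteria".
- Parametric criteria, item 5: "In case of abnormal data distribution generalized linear models and/or mixed linear models will be used".

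Item 6 of Parametric criteria adds: "Selection of the type of distribution, specification of factor and covariance structures of the model will be made using fit-statistics such as AIC". It lists no candidate distributions or factors, and its wording leaves the choice of fit statistic open as well.

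The outcomes concerned, under Secondary Outcome Measures, are temperature change (2), symptom severity scores (5), area under the severity curve (7) and the immune parameters (11-14).

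**The concern.** A variable that fails the pre-test is sent to a rank test by one section and to a regression model by another. The two answer different questions. Mann-Whitney asks whether values in one arm tend to be larger than in the other; a gamma model with log link compares means as a ratio. They can differ on significance for the same data.

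The pre-test and the fit statistics can be computed only from the outcomes. The plan requires no blinded selection step, and Study design describes the trial as open-label. Whoever analyses the data could therefore settle the route with the results in hand.

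The rank branch has a further gap. Friedman tests change over time within patients and does not compare the two arms. For repeated outcomes, that branch supplies no between-arm test of the time course.

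At stake is how the main continuous efficacy results and the immunology results can be read.

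**Working it through.** **1. The rules side by side, for a variable that fails the pre-test**

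| Question | Statistical criteria and Non-parametric tests | Parametric criteria, items 5-6 |
|---|---|---|
| Two arms, one value per patient | Mann-Whitney | Generalized and/or mixed linear model |
| Change over time | Friedman (within patients only) | Generalized and/or mixed linear model |
| Distribution and factors | Not applicable | Chosen by fit statistics |
| Which rule takes precedence | Not stated | Not stated |
| Tied to an endpoint | No | No |

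**2. Inputs.** Evaluation of sample size gives 79 per arm and a type 1 error of 5%. The plan states no figure for this particular point, so there is none to reproduce. It gives no means or standard deviations for these outcomes, so every distribution below is an assumption.

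**3. How often the conflicting branch is reached.** With 79 values and the Lilliefors form of Kolmogorov-Smirnov, the pre-test rejected in:
- 98.5% or more of samples for Poisson-type scores with mean 4 or less, and in 100% for a 0-3 fever score
- about 75% at mean 8
- 51% at mean 12
- 35% at mean 16

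So the branch is common for low scores and less so for high ones.

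**4. Error when there is no effect, Mann-Whitney against a gamma log-link model.** Gamma outcomes with shape 0.5, 1 and 2, 79 per arm, 4,000 data sets each:
- each route alone: 4.9-6.0% across repeat runs
- the two disagree on significance: 3.6-5.9%
- at least one is significant: 7.4-8.0% (7.4-8.7% across repeat runs)

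**5. Does selection by AIC cost error by itself?** A separate simulation used 2,000 trials per row and 79 per arm. The lowest-AIC model came from an assumed set: gamma, log-normal and normal, each with and without baseline.

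| Assumed data | Mann-Whitney significant | Lowest-AIC model significant | Disagree | Either significant |
|---|---|---|---|---|
| Log-normal, no effect | 5.1% | 4.8% | 5.1% | 7.5% |
| Gamma, no effect | 4.7% | 5.05% | 5.25% | 7.5% |
| Log-normal, effect -0.3 (log scale) | 54.2% | 67.3% | 20.25% | 70.9% |
| Gamma, effect -0.3 (log scale) | 54.8% | 75.8% | 25.75% | 78.2% |

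The columns can be checked against each other, since P(either) = [P(A) + P(B) + P(disagree)] / 2. First row: (5.1 + 4.8 + 5.1) / 2 = 7.5. Second row: (4.7 + 5.05 + 5.25) / 2 = 7.5.

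The simulation standard error at 7.5% is √(0.075 × 0.925 / 2,000) = 0.6 percentage points, so an excess of 2.5 points over 5% is not noise.

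Selection by AIC alone stays at about 5%. The excess comes from leaving open which route is reported. In the two effect rows, part of the gap arises because the model could use the baseline value and Mann-Whitney could not.

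**The case against.** The strongest reply is that the 7.5-8% is a union rate. It assumes that both routes are run and the significant one is reported, and no section permits that. This stands. A reader might infer that the 5% level is lost, or that AIC selection inflates error. The documents do not support either: each route alone stays near 5%, and so does the AIC-chosen model. What remains is that the plan does not rule the choice out.

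A second reply is that the sections can be read together, with rank tests for single comparisons and models for time courses. That reading is sensible, but it is not written, and listing Friedman for time changes cuts against it.

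Several stronger readings also go too far:

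- That scores nearly always fail the pre-test. The rejection rate falls to 35% at a mean of 16 under the same Poisson assumption, and the plan gives no score means.
- That adding a log-normal model as a further reportable route pushes the rate higher. The plan names no such route.
- That AIC cannot compare factor sets. This depends on the estimation method, which the plan does not state.
- That the analysts will know the arms. Open-label describes treatment; the plan does not say whether analysts are blinded.
- That symptom duration (6) is caught too. Item 5 of Non-parametric tests may send it to survival analysis.

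The gamma figures also do not fit every outcome. Symptom scores can be zero, which a gamma model cannot take. Study design leaves blood sampling for immunology to the investigator's judgement, so 79 per arm may not apply to outcomes 11-14.

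**Conclusion.** The point holds as a conflict between two stated rules, and not merely as missing detail. It covers secondary outcomes 2, 5, 7 and 11-14 when they fail the pre-test.

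Under assumed skewed positive outcomes with 79 per arm, an unresolved choice between Mann-Whitney and a gamma model raises the false-positive rate from about 5% to about 7.5-8%. Under an assumed moderate effect, Mann-Whitney and the AIC-chosen model disagree on significance in 20-26% of trials. These sizes rest on the assumed distributions, baseline correlation and effect.

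The proper conclusion is that 5% is not assured for these outcomes. A reader might extend this to the main comparison, but the primary outcome is a proportion and items 5-6 do not bear on it in this way. The change should be made, but the primary analysis does not depend on it.

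**What to change.** - Delete the normality gate, the line under Statistical criteria that depends on it, and item 5 of Parametric criteria.
- Limit item 6 to choosing among covariance structures that are named in advance.
- For repeated outcomes (2, 5, 11-14), fix in advance one between-arm model with arm, day and arm-by-day terms. Justify it by the approximate normality of mean differences at about 79 per arm. It should not be presented as a cure for non-normality, because a linear mixed model itself assumes normal residuals.
- For the area under the curve (7), use the between-arm mean difference with a 95% interval.
- Name Mann-Whitney with the Hodges-Lehmann shift as the single sensitivity analysis, and say that it cannot replace the main analysis. Without that sentence the problem returns: under the same null, the mean difference and Mann-Whitney together give 7.3-8.0% if either may be reported.
- List by name the laboratory variables to be log-transformed and say how zeros are handled. Do not decide this from observed skewness.

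The cost is wording only, with no added patients or visits. The downside is that the analyst loses the freedom to refit after seeing the data.
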